One limitation of current AID systems is that they have no knowledge about the context or environment that a person is currently experiencing. Contextual patterns can potentially improve the performance of an AID by recognizing environments or patterns of living that are related to changes in glucose. The team at OHSU is developing a context-aware glucose prediction algorithm that will capture context data from the patient both indoors and outdoors. This context data will be provided to the algorithm to allow for detecting contextual patterns that might relate to hypo- or hyperglycemia. The goal of this study will be the creation of a data set that will include contextual patterns along with glucose, insulin and physiological data. Participants will complete meals and exercise at specific times. The purpose of the prescribed meals and exercise sessions is to generate ground truth patterns that will be used in the design of the context-aware glucose prediction algorithm.

Primary Objective

- To assess the accuracy of the context-aware glucose prediction by comparing glucose prediction values against the Dexcom G6 CGM values using mean absolute relative error (MARE)
- To assess the accuracy of the context-aware glucose prediction by comparing glucose prediction values against the Dexcom G6 CGM values using mean relative error (MRE).

Study Hypothesis:

- The study hypothesis is that context pattern data will improve the accuracy of the prediction of hypoglycemia and hyperglycemia in the context-aware glucose prediction algorithm.

Primary Endpoints:

- Comparison of the accuracy of hypoglycemia prediction comparing glucose prediction values against the Dexcom G6 CGM values using mean absolute relative error (MARE).
- Comparison of the accuracy of hypoglycemia prediction comparing glucose prediction values against the Dexcom G6 CGM values using mean relative error (MRE).

Study Type

This is a single center randomized prospective study measuring the accuracy of the context-aware glucose prediction against the Dexcom G6 CGM values.

Study Population

[figure not shown]
Study population will be adults with type 1 diabetes, ages 18 – 65 years of age. Older subjects are excluded due to higher risk of unrecognized coronary artery disease. Younger subjects are excluded as it is appropriate to assess safety and efficacy first in the adult population. Thirty subjects will be recruited to participate in studies.

Protocol Summary:

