Subjects will be on study for 28 days. Sensor glucose, activity, exercise, insulin, indoor and outdoor contextual patterns and meal data will be collected during this time. Subjects will wear the Dexcom G6 CGM system and a FitBit Ionic (or similar FitBit), Polar, Garmin or Apple Watch physical activity monitor for the entire 28 days. Physical activity monitors will send data to the iPancreas mobile app created by OHSU. iPancreas will be supplied to participants on a separate study-provided phone. Subjects will continue to use their own insulin pump. Subjects will be asked to also wear a MotioWear indoor/outdoor context-aware tracking tag and to install the MotioWear beacons within their home. Subjects will be randomized to complete either aerobic, high intensity interval training, or resistance exercise videos twice weekly at home during weeks 1 and 2 and once weekly during weeks 3 and 4. Subjects will also ingest a self-selected meal prior to these prescribed exercise sessions. Subjects will consume a high carbohydrate dinner once each week on the same day, at approximately the same time (but not on the exercise days).

Subjects will use the T1 DEXI mobile app created by OHSU to capture meal and exercise data along with photos of meals over the 28 day period. Subjects will take photos of their food the day of and the day after they complete the exercise video. While at home, subjects will check CBG before and after exercise, for symptoms of hypoglycemia, and for Dexcom G6 alarms for sensor <70 mg/dL and >250 mg/dL. See **Figure 1** below for a diagram of the study flow. The study investigators retain the authority to modify any aspects of the protocol at his/her discretion if he/she believes the subject's safety is a concern.

Figure 1: Study Flow Design

Background on MotioWear System

Our group at OHSU has developed a unique context measurement system in collaboration with MotioSens (Portland OR) called MotioWear. MotioWear (Figure 2) is comprised of a wearable tag, beacons that are plugged in around a home, and a data hub that captures the movement

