Up to 75 subjects may be screened in this study. Goal enrollment is 30 subjects.

Withdrawal Criteria

The subject may withdraw at will at any time or at the discretion of the Investigator.

A subject must be withdrawn if the following applies:

1. Hypoglycemia during the treatment period posing a safety problem as judged by the investigator.
2. Hyperglycemia during the treatment period posing a safety problem as judged by the investigator.
3. Protocol deviation having influence on efficacy or safety data as judged by the Investigator.
4. Substantial and repeated non-compliance with trial procedures.
5. Pregnancy.
6. Intention of becoming pregnant.

Visit Procedures

Staff will confirm participant and household do not have COVID-19 or symptoms of COVID-19 prior to conducting any face-to-face visits. In order to minimize face to face contact with participants per OHSU Covid-19 policy, there is the option to complete some visits virtually.

Screening (Visit 1)

Screening will take place within 12 weeks prior to Visit 2. All screening visits will take place at OHSU's Oregon Clinical Translational Research Institute (OCTRI) outpatient clinic, the

Biomedical Engineering Point of Care (BME POC) Laboratory or at the Harold Schnitzer Diabetes Health Center. The subject will be sent the consent form prior to the screening by email so that they can have time to read it fully at their leisure and prepare any questions they might have. Upon arrival at the clinic and prior to any procedures, study staff will explain the study, give the subject ample time to ask questions and consider participation, and ensure that subject voices understanding of the informed consent and study requirements. To minimize the possibility of coercion and to ensure that subject is signing the appropriate version of consent, an informed consent checklist will be used by study staff. After the subject has signed the consent, a copy of the consent/authorization form will be given to the subject. The original will be kept for the source document.

A capillary blood glucose (CBG) will be obtained and measured by a Contour Next glucose meter and recorded after consenting. Prior to measurement of any blood samples, the meter will undergo quality control testing with two different glucose levels, one high and one low, and both values must fall within the accepted range for a meter to be used.

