Statistical methods

The hypothesis of this study is that we will be able to identify contextual patterns in the movement data that will relate to glycemic outcomes. We will use machine learning techniques

including k-means clustering and Gaussian mixture models to group contextual patterns and then relate these groups of patterns with glycemic outcomes including the following:

- Time in hypoglycemia (<70 mg/dL)
- Time in hyperglycemia (>180 mg/dL)
- Time in a target range (70-180 mg/dL)
- Mean glucose
- Glucose variability (standard deviation and coefficient of variance).

We will evaluate if the clusters of contextual patterns are related to differences in glycemic outcome measures using generalized estimating equations, which takes into account correlated data and repeated measures. Data will be analyzed using an intention-to-treat analysis and missing sensed glucose values will be interpolated for up to 20 min segments.

Confidentiality and Protection of Human Subjects

RISKS and BENEFITS

Risks: The risks of the protocol procedures are considered minor. Subjects will be managing their own blood glucose as they normally would.

Risks from exercise include falls, sprains, bruises, very low risk of bone fractures and head trauma. The likelihood of significant harm is quite low.

There is a small risk of sensor fracture, and in such a case, a piece of the sensor could be left in the tissue after sensor removal. For this reason, the study investigator will inspect each removed sensor for the possibility of breakage or fracture. Any evidence of sensor breakage will be recorded and reported to the sensor company.

Benefits: The subject may not directly benefit from being in this study; however, their participation may help to advance automated insulin decision support software.

COSTS:

Subjects will receive \$500 for completion of all study visits. If subjects withdraw early from the study, compensation will be given as follows: \$125 per 7 study days in the study. If the subject completes a partial week, the subject will also receive \$125 for the partial week. There is no compensation for the screening visit. Additional reimbursement will be available for participants who complete protocol requirements to help compensate for their time. The payment amount will be specified in the informed consent form.

Monitoring Entity:

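### The 20-minute interpolation rule does not exempt the MARE/MRE endpoints; if it is applied to them, forecasts issued in a gap use later glucose and MARE comes out too low

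*Combined protocol and SAP*

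**What the plan says.** The combined protocol and SAP has one statistical section, Statistical methods. It closes with the only rule on missing sensor data: "missing sensed glucose values will be interpolated for up to 20 min segments". The interpolation method is not named, longer gaps are not covered, and no analysis is singled out or exempted. The sentence before the one containing this rule concerns the cluster analysis: "We will evaluate if the clusters of contextual patterns are related to differences in glycemic outcome measures using generalized estimating equations". The section does not mention forecasts, MARE or MRE.

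The primary measures stand under Primary Endpoints, where hypoglycemia prediction is judged by "comparing glucose prediction values against the Dexcom G6 CGM values using mean absolute relative error (MARE"). MRE is a second endpoint in the same form. The Study Hypothesis is that "context pattern data will improve the accuracy of the prediction of hypoglycemia and hyperglycemia". The opening text states: "The goal of this study will be the creation of a data set", and the data are to serve algorithm design, so forecasts may be generated afterwards from a completed glucose series. The prediction horizon, sampling interval, expected share of missing readings and expected MARE are not given.

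**The concern.** Interpolating a short gap is reasonable for a retrospective summary such as time in range. A prediction endpoint differs in two ways.

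- **Inputs.** A filled value inside a gap depends on the first reading after it. A forecast issued in the gap from filled inputs has seen part of the future.
- **Reference.** If the target time falls in a gap, the forecast is scored against a constructed value, while the endpoint is defined against Dexcom G6 values.

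Both tend to flatter MARE, and in a retrospective run neither would be visible in the results. At stake is whether the reported MARE is one that the algorithm could reach in use.

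**Working it through.** The plan has no figure to reproduce. The check has three parts: how far the leak reaches, its size in affected forecasts, and its size overall. Apart from the 20-min limit, every numerical input is assumed.

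**1. Reach of the leak.** With L missing readings and linear filling, the k-th filled value is G_before + k/(L+1) × (G_after − G_before). For L = 4 the later reading has weight 1/5, 2/5, 3/5 and 4/5. With 5-min readings it lies up to 20 min ahead for L = 4 and up to 15 min ahead for L = 3. Once the later reading has arrived, filling the gap behind it uses nothing from the future. Only forecasts issued inside the gap leak.

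**2. Affected forecasts, 30-min horizon.** Two simulations with linear predictors were run.

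*Simulation A:* smooth glucose series, three missing readings between observations 20 min apart. MARE from complete data was 12.1%.

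| Missing reading | Filled inputs | Past-only inputs | Below past-only | Below complete data |
|---|---|---|---|---|
| 1st | 6.7% | 14.0% | 7.3/14.0 = 52% | 5.4/12.1 = 45% |
| 2nd | 9.0% | 15.8% | 6.8/15.8 = 43% | 3.1/12.1 = 26% |
| 3rd | 11.1% | 17.4% | 6.3/17.4 = 36% | 1.0/12.1 = 8% |

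*Simulation B:* log-autoregressive glucose (mean about 157, SD about 58 mg/dL), six-lag predictor, four missing readings.

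| Sensor noise SD | Filled inputs | Past-only inputs | Complete data | Below past-only | Below complete data |
|---|---|---|---|---|---|
| 0 mg/dL | 5.18% | 9.06% | 6.54% | 3.88/9.06 = 43% | 1.36/6.54 = 21% |
| 3 mg/dL | 6.63% | 10.12% | 7.81% | 3.49/10.12 = 34% | 1.18/7.81 = 15% |

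Shorter gaps leak less. In B, three missing readings give 37% (8.60 to 5.38) and 29% (9.68 to 6.83) below past-only. One missing reading gives 24% (7.62 to 5.82) and 16% (8.79 to 7.36).

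In both simulations, filled inputs beat complete data. Losing data cannot honestly improve a forecast, so this is a sign of look-ahead.

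*Scoring against filled values* (B, same gap and horizon): 6.58% against true values becomes 6.20%, and 7.97% becomes 7.47%. That is 0.38 and 0.50 points. Over all settings of B (horizons of 15, 30 and 60 min, one to four missing readings) the reduction was 0.1 to 0.5 points, against 1.1 to 4.5 points for leaked inputs.

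**3. Overall MARE.** If a share p of readings lies in such gaps, overall MARE falls by about p × (input effect + scoring effect).

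- B, 30 min, four missing, p = 1%: 0.01 × (3.88 + 0.38) = 0.043 and 0.01 × (3.49 + 0.50) = 0.040 points. At p = 5% this is about 0.2 points and at 10% about 0.4, on a MARE of about 6.5 to 8%.
- B, all settings, p = 1%: from 0.01 × (1.08 + 0.11) = 0.012 to 0.01 × (4.34 + 0.53) = 0.049 points.
- A, inputs only, p = 1%: mean difference (7.3 + 6.8 + 6.3)/3 = 6.8 points, so 0.068 points on 12.1%. As a proportion this matches B: 0.068/12.1 = 0.6%, against 0.043/6.54 = 0.7% and 0.040/7.81 = 0.5%.
- If the alternative is to issue no forecast in a gap, complete data are the comparator. B then gives 0.01 × (1.36 + 0.38) = 0.017 and 0.01 × (1.18 + 0.50) = 0.017 points per 1%.

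**The case against.** The strongest reply is that the plan does not describe the procedure criticised. The rule closes a paragraph on clusters, glycemic outcomes and generalized estimating equations, and may have been meant only for them. A reader might infer that forecasts will be issued and scored on filled data, so that the primary results will be inflated. The documents do not support that, because they never say which series the forecasts use. What remains is that the rule is general, is the only one, and exempts nothing. If it was meant for the cluster analysis alone, the primary endpoints have no missing-data rule, and a sentence is needed either way.

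A second reply is that the hypothesis implies a comparison with prediction lacking context. Both models would share the leaked glucose inputs, so the bias may partly cancel. That stands for the comparison. It does not protect the absolute accuracy of the context-aware prediction, which is what the Primary Objective asks for.

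A third is that the effect is small and depends on the comparator. This also stands: the 35-50% applies only to forecasts issued in the longest permitted gaps, measured against past-only forecasts, and scoring against filled values adds little.

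**Conclusion.** The point holds as an open risk in the wording, not as a stated error. If the rule is applied to the prediction endpoints, MARE is too low. For forecasts issued in a 20-min gap at a 30-min horizon the shortfall is about 35-50% against past-only inputs and about 8-45% against complete data. Overall it is about 0.01 to 0.05 percentage points per 1% of readings in short gaps across the settings of simulation B, and about 0.07 in simulation A, where errors are larger. These figures rest on assumed 5-min readings, linear filling, simulated glucose and simple linear predictors. The total depends on a gap share that the documents do not give.

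Two further inferences are not supported. MRE need not look better: it is taken here as a signed mean, only MARE was computed, and a smaller absolute error does not imply a signed mean nearer zero. Nor is it shown that the test of the hypothesis would change. The simulations averaged over all glucose levels, so the effect on hypoglycemia prediction, the subject of the Primary Endpoints, is untested. It could be larger if gaps fall around a glucose nadir.

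**What to change.** Amend Statistical methods so that:

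- interpolation of gaps up to 20 min, by a named method, applies only to the glycemic summary outcomes listed there;
- for MARE and MRE, each forecast uses only data available when it is issued, with missing inputs carried or forecast from earlier readings, or else no forecast is issued in a gap (choose one in advance);
- MARE and MRE are scored only where the target is an observed Dexcom G6 reading;
- the share of readings in gaps, the forecasts skipped and the pairs excluded are reported.

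This takes a few sentences and a flag on filled values, with no new data. The price is slightly fewer scored pairs and a slightly less favourable MARE.

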Triggers for reporting unanticipated problems are seizure, hospitalization, death or any other occurrence considered serious by the PI. If ongoing monitoring of the closed-loop studies reveals studies repeatedly being terminated because of unresponsive hyperglycemia or repeated serious hypoglycemia (resulting in altered mental status, loss of consciousness, or seizure) believed not amenable to revisions in control system parameter tuning, then the study will be discontinued immediately. If studies in two subjects are stopped for severe hypoglycemia or severe hyperglycemia, then the entire study will be halted. In addition, if there is any unexpected event such as death or patient hospitalization, the studies will be stopped until the root cause is evaluated.

Any adverse event (AE) and/or unanticipated problem (UP) will be reported to the investigator monitor immediately by one of the investigators. Hypo- and hyperglycemia will not be considered AEs unless subject has positive ketones or displays symptoms of hypoglycemia such as: loss of consciousness, slurred speech, hospitalization or EMS services called. One of the investigators will always be on-call during the closed-loop studies and will write up a description of the adverse event/unanticipated problem. All reportable new information (RNI) will be reported to the IRB within five calendar days after the PI learns of the event. RNI is any information that might meet the regulatory definition of an unanticipated problem involving risks to subjects or others or serious or continuing noncompliance that might impact the criteria for IRB approval. The report will be submitted to the IRB by the principal investigator or study coordinator. A summary of all UP's and adverse events, including those that do not meet the requirement for RNI, will be submitted with the continuing review.

Confidentiality Procedures:

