Appendix B: Devices
FitBit

Garmin Watch

Polar Watch

[figure not shown]
Apple Watch

Dexcom G6 Continuous Glucose Monitoring System which includes Sensor and Sensor Transmitter

Smart phone with T1 DEXI app

Contour Next Blood Glucose Meter

Appendix C: Hypoglycemia Awareness questionnaire: This survey item will be used to categorize awareness or having reduced awareness of hypoglycemia.

1. Check the category that best describes you: (check one only)

- I always have symptoms when my blood sugar is low (A)
- I sometimes have symptoms when my blood sugar is low (R)
- I no longer have symptoms when my blood sugar is low (R)

2. Have you lost some of the symptoms that used to occur when your blood sugar was low?

- Yes (R)
- No (A)

3. In the past 6 months how often have you had moderate hypoglycemia episodes? (Episodes where you might feel confused, disoriented, or lethargic and were unable to treat yourself).

- Never (A)
- Once or twice (R)
- Every other month (R)
- Once a month (R)
- More than once a month (R)

4. In the past year, how often have you had severe hypoglycemia episodes? (Episodes where you were unconscious or had a seizure and needed glucagon or intravenous glucose?)

- Never (A)
- 1 time (R)
- 2 times (R)
- 3 times (R)
- 4 times (R)
- 5 times (R)
- 6 times (R)
- 7 times (R)
- 8 times (R)
- 9 times (R)
- 10 times (R)
- 11 times (R)

- 12 or more times (R)

5. How often in the last month have you had readings < 70 mg/dl with symptoms?

- Never
- 1 to 3 times
- 1 time/week
- 2 to 3 times/week
- 4 to 5 times/week
- Almost daily

6. How often in the last month have you had readings < 70 mg/dl, without symptoms? R: 5<6, A: 6<5;

- Never
- 1 to 3 times
- 1 time/week
- 2 to 3 times/week
- 4 to 5 times/week
- Almost daily

7. How low does your blood sugar need to go before you feel symptoms?

- 60-69 mg/dl (A)
- 50-59 mg/dl (A)
- 40-49 mg/dl (R)
- < 40 mg/dl (R)

8. To what extent can you tell by your symptoms that your blood sugar is low?

- Never (R)
- Rarely (R)
- Sometimes (R)
- Often (A)

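### Hypo- or hyperglycemia that forces withdrawal, and severe hyperglycemia that counts toward the two-subject halt, can fall outside the adverse event definition

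*Combined protocol and SAP*

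**What the plan says.** Three rules bear on the same kind of event.

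- **Withdrawal Criteria, items 1 and 2.** A subject must be withdrawn for "Hypoglycemia during the treatment period posing a safety problem as judged by the investigator" and likewise for "Hyperglycemia during the treatment period posing a safety problem as judged by the investigator". The test is the investigator's judgment alone.
- **Monitoring Procedures, halting.** "If studies in two subjects are stopped for severe hypoglycemia or severe hyperglycemia, then the entire study will be halted". The rule does not define severe and does not refer to AE status.
- **Monitoring Procedures, AE definition.** "Hypo- and hyperglycemia will not be considered AEs unless subject has positive ketones or displays symptoms of hypoglycemia such as" four examples, which the sentence then names. No exception is made for an event that led to a withdrawal or a stop. The examples are "loss of consciousness, slurred speech, hospitalization or EMS services called".

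Two reporting provisions in the same section matter as well. Unanticipated problems are triggered by a seizure, a hospital admission, a death, or whatever else the principal investigator regards as serious. Continuing review receives a summary of unanticipated problems and AEs, "including those that do not meet the requirement for RNI, will be submitted with the continuing review".

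**The concern.** Keeping routine glucose excursions out of the AE record is sensible in type 1 diabetes. The exclusion as worded goes further. It also covers events that the protocol itself treats as grave enough to remove a subject or, for hyperglycemia, to count toward stopping the study. Apart from ketones, the only way into AE status is through symptoms of hypoglycemia, which do not describe a hyperglycemic event.

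What is at stake is the safety record, not the prediction-accuracy endpoints. A body reviewing the summary of AEs and unanticipated problems would expect to find there the reason a subject was withdrawn on glycemic safety grounds. As written, whether it appears can depend on a discretionary classification. Monitoring Entity assigns monitoring to the principal investigators themselves, and no independent monitor is described who might notice the omission.

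**Working it through.** The plan gives no figure to reproduce, and no arithmetic applies. The check asks whether one event can satisfy the withdrawal or halting rule and still fall outside the AE definition.

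**Inputs**

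- Withdrawal (Withdrawal Criteria 1 and 2): investigator judgment; no ketone or symptom condition.
- Halt (Monitoring Procedures): two subjects stopped for a severe event; severe undefined; no link to AE status.
- AE status (Monitoring Procedures): positive ketones, or symptoms of hypoglycemia. The four examples follow the words for an illustrative list, so the list is open.
- Nearest descriptions of grave hypoglycemia: a separate discontinuation rule in Monitoring Procedures refers to "repeated serious hypoglycemia (resulting in altered mental status, loss of consciousness, or seizure", and the screening questionnaire in Appendix C describes severe episodes as "Episodes where you were unconscious or had a seizure and needed glucagon or intravenous glucose".
- Ketone testing: ketones appear only in the AE sentence, and no ketone test is described in the text available.

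**Cases**

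| Event | Withdrawal | Counts toward halt | AE |
|---|---|---|---|
| A. Hyperglycemia, ketones negative or untested, none of the listed signs | Yes, if judged a safety problem | Yes, if a subject is stopped and it is called severe | No |
| B. Hyperglycemia, ketones positive | Yes, if judged a safety problem | Yes, if a subject is stopped and it is called severe | Yes |
| C. Hypoglycemia without symptoms | Yes, if judged a safety problem | Not under the nearest descriptions | No |
| D. Hypoglycemia with unconsciousness, seizure or altered mental status | Yes, if judged a safety problem | Yes, if a subject is stopped | Usually yes |

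Case A is the firm one. It needs no assumption about hypoglycemia and would remain even if ketones were tested routinely, because a negative result leaves the event outside the definition. A generous reading might let a hospital admission or emergency call bring hyperglycemia in, but that still leaves hyperglycemia managed without either.

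Case C is plausible. Subjects check capillary glucose when the sensor alarms below 70 mg/dL, so lows without symptoms will be detected. Exclusion criterion 6 excludes on the questionnaire score only at four or more reduced-awareness answers, so the score alone admits a subject with up to three (the investigator may still exclude on judgment).

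Case D shows where the gap mostly closes. Loss of consciousness is a named example, and altered mental status and seizure fit naturally within an open list.

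**Following cases A and C to the report.** They are not AEs, so they reach the continuing-review summary only as unanticipated problems. None of the three named triggers need be present, which leaves the principal investigator's view of seriousness. The protocol also describes detecting unanticipated problems largely through assessment of adverse events, so losing AE status weakens that route. The form list under Recording of Data has seven entries, including AE, serious AE and study completion forms, but none named for withdrawal or early termination.

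**The case against.** The strongest reply is that the three rules serve different purposes and can all be obeyed at once. Withdrawal is also mandatory for matters that are not inherently AEs, such as non-compliance or an intention to become pregnant. That stands: this is a gap in recording, not a set of rules that cannot be followed together.

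Second, a reader might infer that the study could be halted for hypoglycemia with nothing in the AE record. That would require severe to mean a glucose value alone. No passage says so, and both nearby descriptions point to events that would usually be AEs.

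Third, a reader might infer that the continuing-review summary would necessarily omit these events, or that the count behind a halt could not be rebuilt. Neither is shown. The summary covers unanticipated problems as well as AEs, and an investigator who stops a subject for a severe event may well call it serious. Sensor and meter data are kept, time below 70 and above 180 mg/dL are planned outcomes, there is a study completion form, and early-withdrawal payment depends on days in the study. The form list is not stated to be exhaustive. These records lessen the harm. But glucose values do not record the judgment that an event was a safety problem, and the protocol does not say that the completion form captures a reason for withdrawal.

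Fourth, the halting rule follows a sentence about closed-loop studies and control-system tuning, although subjects here use their own pumps, so how far it was meant for this study is unclear. That weakens the halting part of the point but leaves the withdrawal part untouched.

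**Conclusion.** The point holds in a limited form. The AE exclusion has no exception for glycemic events that cause mandatory withdrawal or count toward the halt. Hyperglycemia with negative or untested ketones can do both without being an AE; symptom-free hypoglycemia can do the first. The continuing-review summary could therefore omit such an event unless the principal investigator classes it as an unanticipated problem.

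A reader might go further and infer a study halted with no trace of the reason. Only the hyperglycemia route comes near that. It would need two stopped subjects, both events called severe, neither with positive ketones nor otherwise qualifying as an AE, and neither classed as an unanticipated problem. Even then, other study records would remain.

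The size cannot be put as a rate, because the documents give no expected frequency of glycemic withdrawals. The number of events affected is at most the number of glycemic withdrawals and stops among the planned 30 subjects. The conclusion rests on reading the AE sentence literally and, for the halting part only, on the halting rule applying to this study. The change is worth making because it concerns safety reporting and costs little.

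**What to change.** The AE definition in Monitoring Procedures must be reconciled with Withdrawal Criteria 1 and 2 and with the two-subject halt. One sentence after the AE definition is enough:

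*Any hypo- or hyperglycemia that leads to withdrawal under Withdrawal Criteria 1 or 2, or that is counted toward the two-subject halt, is recorded on the Adverse Event form and included in the AE summary, whatever the ketone or symptom status.*

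Routine excursions stay outside the AE record, and the withdrawal and halting rules are not altered. Because the sentence refers to events actually counted toward the halt, AE recording would no longer depend on how severe is read. The cost is a few extra AE forms and a reported AE count that may look slightly less favourable.
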